The 28-day behaviour change practice includes two sequential parts. The first part consists of bringing mothers and their moderately malnourished child together in a home-like setting (the Hearth) for a period of 2-weeks to rehabilitate their malnourished child and learn improved feeding, hygiene, and caregiving practices. The Hearth sessions delivered over 14 days (6 hearth days plus 1 rest day/wk), and each session will last approximately 2.5 hrs. The second part consists of mothers practicing the learned behaviours in their home for another 2-weeks with support from the study staff. The Hearth/follow-up home visit model is based on the work of World Vision, which has shown that for some households, behaviour change, specifically in

feeding, caring, nurturing, and hygiene practices, may take up to 3 cycles to be fully adopted and for the child to regain a normal growth pattern. Hence, for children who do not reach their growth milestones after the first 28-day cycle, we will offer mothers the opportunity to participate in up to 3 cycles of the 28-day programs, with non-responders referred for medical evaluation. This length is deemed optimal to minimize dependency on the external rehabilitation process while allowing mothers the opportunity to “learn by doing”, and subsequently practice the new behaviours at home. The sessions will be facilitated by trained staff, and will emphasize practical learning, including preparing meals based on locally available foods.

Not all households will require 3 cycles; those whose children achieve the desired weight gain of 400 g (as recommended by WHO guidelines) may graduate earlier. This model is not intended to treat acute malnutrition or wasting but rather to address chronic malnutrition resulting from inadequate feeding and caregiving practices, which requires sustained engagement to reverse.

Following the hearth sessions, mothers will continue with a 14-day at-home practice period, during which they apply the newly learned behaviours in their household setting. Study staff will visit each home three times a week for 1.5 hours to reinforce behaviours, monitor child growth, and provide ongoing support.

If after each 28-day cycle the child meets their growth milestones, home visits will shift to monthly check-ins for up to 6 months. If the child falls short of meeting the growth milestone, families will be invited to repeat the 28-day Hearth and home practice cycles up to three times.

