Anthropometric data will be collected by trained study staff to measure children's height and weight. Measurements will be taken with calibrated tools to minimize observer bias, and analyzed using WHO Anthro software to determine nutritional status based on standard Z-scores (weight-for-age, height-for-age, and weight-for-height). Children will be classified as underweight, stunted, wasted, or well-nourished. For the Treatment and Control Arm children, anthropometric measurements will be obtained at the time of recruitment, part of the baseline survey, during monthly follow-up, and part of the endline survey. Additionally, for the children in the Treatment Arm, weight will be collected during the 28-day behavior change practice program (Days 1, 13, and 28).

Inclusion Criteria

INTERVENTION PHASE

Eligible participants must meet all of the following conditions:

Child-Level Criteria:

- While children in the intervention phase will range from ages 7-23 months, At the time of recruitment children will range from Ages: 7–15 months.
 - Priority will be given to younger children, aged 7–11 months followed up by 12–15 months, to allow completion of the intervention and follow-up visits before the child turns 24 months of age, as complementary feeding refers to feeding practices between the ages of 6–24 months.
 - Moderate malnutrition, defined by: Weight-for-age Z-score between -2 and -3 standard deviations.

Household-Level Criteria:

- Households will be eligible to participate if:
 - They meet the classification of very poor or poor (based on community-defined wealth stratification).
 - Have access to clean water and sanitation.
 - Food secure at time of recruitment, defined as:
 - On government assistant program or at least one adult has permanent employment, or two or more have temporary employment.

- Ownership of at least one simple livestock (e.g., chicken, goat, or sheep).
- Access to a kitchen garden, or willingness to establish one with study support

Mother Eligibility Criteria:

The household is eligible only if the mother meets all of the following:

1. Mother is the primary caregiver for the Index Child (responsible for daily care, including supervision, bathing, and feeding).
2. Mother is alive and at least 18 years old.
3. Mother is currently breastfeeding the Index Child and willing to continue until the child reaches 2 years of age.
4. Mother expresses an interest in participating in the PD/Hearth program.

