4. ELIGIBILITY ASSESSMENT

To determine eligibility for participation, each Index Child will undergo a multi-step assessment process.

- Assessment of the child's nutritional status. Only those children identified as being moderately malnourished admitted into the study. Children will be assessed by the field staff through anthropometric measurements: weight, length/height, and mid-upper arm circumference (MUAC) and using standardized WHO growth reference tools. Children will only be included if they are classified as moderately underweight (weight-for-age Z-score between -2 and -3 SD). Severely malnourished children will be referred immediately to a health facility for medical care. All measurements will be conducted by trained staff following strict protocols to ensure consistency and accuracy.

To be eligible for the Treatment Arm. All children meeting the classification of moderate malnutrition will undergo a complete medical at the local health facility, including confirmation of their nutritional status and update of their vaccination record. Eligibility will be determined by working with the Lady Health Worker affiliated with the respective household, who will rule out children with chronic disease according to the exclusion list. A final confirmation from the health facility will be sought after consent is obtained to assess whether the child is well enough to participate in the 28-day behavior change (Hearth) program.

- To be eligible for the Control Arm. All children meeting the classification of moderate malnutrition will be assessed for chronic illness. Initial assessment will be done by asking mothers about their child's health and final eligibility confirmed by Lady Health Workers' medical records.
- Assessment of the household eligibility. Households will undergo an assessment of their wealth ranking and food security status. Study staff will use the Final Recruitment Screening Form to confirm and document eligibility for participation. The recruitment forms for both the treatment and control arms are attached in Section 9.5.

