As is typical in Pakistan, the mother of the Index Child will be asked to provide consent by signing the form to confirm her understanding and agreement. If the father is available, the father may also provide consent. In households where literacy is limited, participants will be offered the option to give consent using a thumbprint, in keeping with ethical research standards. Refer to Section 9.2 for the consent forms.

Procedures

PROCEDURES FOR PARTICIPANTS IN THE TREATMENT ARM

28-Day Behavior Change Practice Program.

The study's community-based intervention model consists of a 28-day behavior change practice program: groups session in a home-like setting (Heath) where mothers and the moderately malnourished Index Child (and interested family) will come together to learn new ways of cooking and practicing successful behaviours to rehabilitate their malnourished child., followed by home practice. Each 28-day program cycle consists of two components:

1- Group Hearth Sessions (2 weeks in duration): Mothers and their Index Child will attend the hearth in small groups (typically 15 mother-child pairs). Sessions will focus on knowledge about complementary feeding, active feeding, hygiene, caregiving, and health-seeking behaviours. Mothers will take part in cooking and caring demonstrations, rotating through roles to build hands-on skills. Accompanying family members may participate to support learning and adoption of new behaviours.

2- Home Practice (2 weeks in duration): After the group sessions, field staff will visit each home three times per week to support the mother's practice of newly learned behaviors. Each visit will last approximately 1.5 hours and will reinforce positive changes and problem-solve emerging challenges.

Mothers are expected to contribute some items of their choice to the hearth (e.g., food items for 1-2 children: egg, rice, vegetables, or water, or household materials (e.g., utensils for their child: spoon, cup/ bowl, or soap) to the sessions, ensuring that activities reflect real-life constraints and available resources. It is hoped active participation will promote engagement and help transition practices in the home setting. The project will contribute cooking pots, utensils and most of the food for the 2-week home-like sessions.

Assessment

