Anthropometric Assessment. Each Index Child's weight and height will be measured at the start and end of each hearth session, and at the end of the 2-week home visits (Day 1, Day 13, Day 27 of each cycle). If, by the end of the cycle, the child has not gained at least 400g, they will be invited to repeat the cycle—up to a maximum of three cycles. Children failing to any gain weight between cycles will be referred to a public health facility for medical evaluation. Z-Scores will be calculated to quantify the child's nutritional status. Mid-Upper Arm Circumference (MUAC) will be taken to assess for wasting. During the follow-up period, the child's weight will be monitored monthly for up to six months post-intervention.

Health assessment.

Baseline health assessments will be conducted at local public health facilities within two weeks prior to the first Hearth session for participants in the treatment arm. Each Index Child will receive a full medical examination by a physician, a Hematocrit (Hb) test via finger prick, and verification and updates for routine immunizations.

All children showing "failure to thrive" (e.g., no weight gain or weight loss after a Hearth cycle) will be referred for medical assessment within five days, and accompanied by study staff.

Results of participants' health assessments will not be shared or retained by the research team. This assessment will be conducted solely to confirm that the child meets eligibility criteria and is well enough to participate in the 28-day behaviour change program. This information is sufficient for enrollment purposes, and no medical or health records beyond the anthropometric measurements will be collected, stored, or used as study data

Data collection

Data will be collected using structured tools and include:

Baseline and follow-up household surveys (at 6 months, and possibly 12 months post-intervention if funding permits): surveys will assess 24-hour food recall and indicators on feeding practices, WASH, gender roles, and health-seeking behaviour. Study survey instrument is attached to Section 9.5.

All data will first be recorded on paper and later digitized by trained personnel.

PROCEDURES FOR PARTICIPANTS IN THE CONTROL ARM

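### Calibrated tools cannot minimise observer bias, and nothing stated shields the endpoint weights from staff knowing the arm, the earlier weights or the 400 g figure

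*Protocol*

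**What the plan says.** Under Evaluation, Anthropometric Measurements, the protocol says "Anthropometric data will be collected by trained study staff" and then "Measurements will be taken with calibrated tools to minimize observer bias". Weights are taken in both arms at recruitment, baseline, monthly follow-up and endline. The treatment arm has additional weighings inside the 28-day program.

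The 28-day program overview says of the home-practice period: "Study staff will visit each home three times a week for 1.5 hours to reinforce behaviours, monitor child growth, and provide ongoing support". The treatment-arm procedures call these visitors field staff: "field staff will visit each home three times per week to support the mother's practice". Eligibility Assessment uses the same label for the people who measure: "Children will be assessed by the field staff through anthropometric measurements". That section also gives the only other measurement safeguard: "All measurements will be conducted by trained staff following strict protocols to ensure consistency and accuracy".

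The figure of 400 g appears in two roles. In the treatment-arm anthropometric assessment, a child who "has not gained at least 400g" by the end of a cycle is invited to repeat it. In the Study Hypothesis, the primary comparison is the proportion of children averaging 400 g/month over the first 4 months.

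Under Recruitment Methods (Setting and Sample Size), the intervention households come from three named Union Councils and the control households from three others, with 100 households per arm.

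**The concern.** The protocol recognises observer bias as a risk and then names a safeguard that does not act on it. A calibrated scale gives the right weight if it is read and recorded neutrally. It does nothing about a measurer who knows the arm, remembers or can see the last weight, and has a target in mind. Who takes the weights, and how, is protocol content, so the absence of a statistical analysis plan does not explain the gap.

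The pressure is uneven between arms. Only the treatment arm has coaching, weighings within a cycle and a decision that turns on 400 g. The primary outcome is also a proportion above a cut-off, so a small upward shift in recorded weights in one arm moves children across the line and would look like benefit. An error of this kind in the recorded data cannot be removed at analysis.

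**Working it through.** **What the text establishes**

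| Question | What the protocol shows |
|---|---|
| Does the named safeguard act on observer bias? | No. Calibration acts on the instrument. |
| Do coaching and growth monitoring coincide? | Yes, at the treatment-arm home visits (program overview). |
| Is the same individual said to coach a household and take its endpoint weights? | No. The staff labels are shared (study staff, field staff), and the roles are never separated. |
| Can the measurer know the arm? | Yes. Each arm has its own Union Councils, so the place reveals it. |
| Are blinding, a separate measurer, concealed earlier weights or duplicate readings mentioned? | No. |
| Are there other safeguards? | Trained staff (Anthropometric Measurements) and strict protocols (Eligibility Assessment). Neither addresses knowledge of arm, earlier weight or target. |

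**Two different uses of 400 g.** The cycle rule concerns gain over one 28-day cycle. The endpoint is an average over 4 months, so its cut-off is 4 × 400 = 1,600 g in total. An error of b grams on the last weight acts in full on a cycle decision but shifts the 4-month average by only b/4 g/month.

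**Illustrative size.** The protocol states no figure for this bias, so there is nothing to reproduce. From the protocol come the 400 g/month cut-off and the 4-month period. The following are assumed:

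- average monthly gain is normal, with SD 80, 100 or 120 g/month;
- mean true gain is 200, 300 or 400 g/month, with no true treatment effect;
- every treated child's month-4 weight is read 50 or 100 g too high, and control weights and all baseline weights carry no error.

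Shift in the average: 50/4 = 12.5 and 100/4 = 25 g/month.

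Rise in the treated proportion = Φ((μ + b/4 − 400)/σ) − Φ((μ − 400)/σ).

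Worked example, μ = 300, σ = 80, b = 100: Φ(−75/80) − Φ(−100/80) = 17.4% − 10.6% = 6.9 points (from unrounded values).

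| Mean gain (g/month) | SD | True proportion | Rise, 50 g error | Rise, 100 g error |
|---|---|---|---|---|
| 200 | 80 | 0.6% | 0.3 | 0.8 |
| 200 | 100 | 2.3% | 0.8 | 1.7 |
| 200 | 120 | 4.8% | 1.1 | 2.5 |
| 300 | 80 | 10.6% | 3.1 | 6.9 |
| 300 | 100 | 15.9% | 3.2 | 6.8 |
| 300 | 120 | 20.2% | 3.1 | 6.4 |
| 400 | 80 | 50.0% | 6.2 | 12.3 |
| 400 | 100 | 50.0% | 5.0 | 9.9 |
| 400 | 120 | 50.0% | 4.1 | 8.3 |

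Rises are in percentage points. The effect depends strongly on how close the mean lies to the cut-off: negligible to small at 200 g/month, and material at 300 to 400.

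**The case against.** Four objections have weight.

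*Same person.* A reader might infer that the person who coaches a household also takes its endpoint weights. The protocol does not say so. Study staff and field staff are generic labels, and the overlap in the text is one of staff category and of visits in the home-practice period. What stands is that nothing separates the two roles.

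*Same threshold.* A reader might also infer that staff weigh children directly against the endpoint cut-off. They do not: gain per cycle and the 4-month average are different quantities. Three consecutive cycles last 3 × 28 = 84 days, so on that schedule no graduation decision would rest on the month-4 weight. What stands is that staff work for weeks to a rule using the same figure, and that it applies in one arm only.

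*Other safeguards.* It would be wrong to say that nothing protects the reading. Training and strict protocols are promised, the latter under eligibility. Both arms are to have similar evaluations, and weight is a comparatively objective measure. The data forms are not shown, so whether they display earlier weights is unknown. These points reduce the concern, but none of the stated safeguards acts on knowledge of arm, earlier weight or target.

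*Size.* The calculation shifts every treated reading, which is cruder than selective rounding near a threshold, and all of its inputs apart from the cut-off and period are assumed. That is accepted. It shows sensitivity and is not an estimate of actual bias.

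**Conclusion.** The point holds in limited form. The stated reason is wrong: calibration does not minimise observer bias, and no other stated measure covers the gap for the weights that define the primary outcome. Knowledge of the arm is an inference, but a firm one, since the arms are in different places. The documents do not support a claim that coaches are known to take the endpoint weights, or that the cycle rule and the endpoint are one threshold.

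Under the assumptions above, the spurious rise in the treated proportion is about 0.3-2.5 points at a mean gain of 200 g/month, 3-7 at 300 and 4-12 at 400. Whether the bias would arise at all cannot be told from the protocol. The change is worth making because it is cheap and biased weights cannot be repaired later.

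**What to change.** In Anthropometric Measurements, confine the calibration sentence to instrument error. Then add one procedure, identical in both arms, for the baseline, month-4 and endline weights:

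- The weighing form shows neither earlier weights nor the 400 g figure.
- Two readings are recorded and averaged, and comparison with earlier weights is made only after recording.
- Where the existing rota allows, the measurer is a field worker who did not run that child's Hearth sessions or home visits.
- The protocol states that measurers are not blind to arm and treats this as a limitation. Swapping staff removes the coach's personal stake but cannot hide the arm.

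The cycle rule itself need not change.

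The cost is a changed paper form, slightly longer visits, and some rescheduling or travel of existing staff. With 100 households per arm, the second reading applies to 3 × 200 = 600 weighings, or 3 × 240 = 720 if the 20% buffer is added on top. The protocol gives no staff numbers, and recruitment moves through one Union Council at a time. Separation of roles is therefore asked for only where the rota permits, and no added staff are assumed.

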1. SETTING

The intervention will be conducted in three Union Councils (UCs): Wah Kohna, 139/P, and Rahim Yar Khan Deh. These UCs were purposively selected based on population need and prior engagement during the formative phase. Our recruitment strategy is progressive: we will maximize recruitment from 1 UC first and only move to the next UC when we have maximized recruitment of households from that UC.

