IMPLEMENTATION OF THE INTERVENTION

SUMMARY

The project is now ready to move into the intervention, informed by the formative research phase, aligned with Objective #3. The intervention targets households with moderately malnourished children between 7 and 15 months of age, and will follow and support these households for a period of 6-months. Consent will be obtained from mothers via thumbprint or signature. Severely malnourished children, regardless of group, will be referred to local health facilities for care. Households in the control group will continue with their usual feeding and care practices.

This study is rooted in an asset-based approach grounded in the belief that in every community there are certain individuals whose uncommon behaviours enable them to find solutions to prevalent and seemingly intractable problems. The intent of the formative research phase supported by the CAC was to learn what is already possible within the community of Rahim Yar Khan and to amplify these strategies to the wider community during the intervention phase. The intervention comprises of two major components: community sensitization and a 28-day behaviour change period.

COMMUNITY SENSITIZATION OVERVIEW

The community sensitization events will be held in each intervention cluster. These events will introduce the project to local families about complementary feeding for children 6-23 months of age. These sessions will be delivered using town-hall format with small group activities. Key messages supported with visuals and print materials from the 28-day behavior change program (discussed below) will be shared with the larger community. The objective of the community sensitization programs is to create community awareness about the project, share best practices related to complementary feeding with the wider community with the hope this will promote community buy-in as well as community and neighborhood support for households participating in the 28-day change program.

28-DAY BEHAVIOR CHANGE PRACTICE PROGRAM OVERVIEW

Prior to recruitment and starting the 28-day behavior change program, each child will undergo a health check by a physician at the local health facility, including anemia screening, and ensuring they are up to date with all required immunizations.

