2. SAMPLE SIZE

We aim to recruit 100 households in the intervention group. Similarly, for the comparison group (Control Arm) we will conduct the study in three UCs: Kot Mehdi Shah, Balouqi Wali, and Ameen Garh, and recruit 100 households in the comparison group-Based on power calculations 100 households in each of the groups will allow us to detect a meaningful difference in child weight gain (≥ 400 grams) with 80% power. To address potential attrition, we are building in a 20% buffer.

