3. GATEKEEPERS

Lady Health Workers (LHWs) will act as trusted intermediaries, identifying eligible households and introducing the study to the households. For villages, tibbas, or basties not previously included in the FGDs or PDIs, the research team will collaborate with the CAC and local community leaders to raise awareness about the study. Public announcements and town hall meetings will be organized to inform community members. Interested households will be encouraged to register their names with designated gatekeepers, who will then share this information with the recruitment team.

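### Arm and area coincide, with intervention Union Councils hand-picked and control ones unexplained, so the between-arm comparison cannot separate an intervention effect from area differences

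*Protocol*

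**What the plan says.** Protocol, Recruitment Methods, 1. Setting, names the intervention areas ("The intervention will be conducted in three Union Councils (UCs): Wah Kohna, 139/P, and Rahim Yar Khan Deh") and gives the reason for choosing them: "These UCs were purposively selected based on population need and prior engagement during the formative phase". Recruitment there is sequential: "we will maximize recruitment from 1 UC first and only move to the next UC" once the first is exhausted.

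Protocol, Recruitment Methods, 2. Sample Size, names the control areas: "for the comparison group (Control Arm) we will conduct the study in three UCs: Kot Mehdi Shah, Balouqi Wali, and Ameen Garh". It gives no reason for that choice, no matching rule, and no statement of whether those UCs took part in the formative phase.

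Protocol, Recruitment Methods, 3. Gatekeepers, shows that earlier contact with the study varies by place, since it makes separate arrangements as follows: "For villages, tibbas, or basties not previously included in the FGDs or PDIs". It does not say in which arm those places lie.

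The Study Overview states the primary hypothesis as a comparison of intervention with control in the proportion of children averaging 400 g/month over the first four months. Objective 4(b) compares average weight gain between the groups. The Evaluation section says that this will establish the intervention's effectiveness. None of these places calls the comparison non-randomised or limits what may be concluded.

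**The concern.** Two features used to pick the intervention UCs can bear on the outcome. Population need is related to how children grow. Prior engagement may be related to uptake, attendance and the way mothers report practices. If the control UCs differ on either, that difference enters the between-arm contrast in full.

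The complete overlap of arm and area makes this hard to repair. Within a UC there is nobody in the other arm, so no analysis can estimate a UC effect and an intervention effect separately. Recruiting more households sharpens the estimate of the combined quantity and does not split it. This is a question of bias, distinct from the loss of precision that comes with few clusters.

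At stake is the primary between-arm conclusion, which as written would be an unqualified statement about effectiveness.

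**Working it through.** **Step 1. The allocation, side by side.**

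| | Intervention | Control |
|---|---|---|
| UCs | Wah Kohna, 139/P, Rahim Yar Khan Deh | Kot Mehdi Shah, Balouqi Wali, Ameen Garh |
| Basis for choice | Need and prior engagement | Not stated |
| Formative-phase status | Engaged (part of the basis for choice) | Not stated |
| UCs shared with the other arm | None | None |

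Arm is a function of UC. In a model of weight gain with an arm term and a term for each UC, the arm term is a linear combination of the UC terms and is not identifiable without further assumptions. Because UCs are filled one after another, the intervention arm could come from fewer than three.

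**Step 2. What the entry rules and baseline data can do.** Both arms use the same weight-for-age band (Z-score between -2 and -3), the same age range (7–15 months at recruitment) and household screening. Both have baseline surveys and monthly weights. These reduce differences between households. They do not reach UC-level conditions or earlier contact with the study. Wealth class follows the community's own stratification, so poor need not mean the same absolute level in every UC.

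**Step 3. Illustration of size.** The protocol gives no standard deviation, control success rate, significance level or UC difference, so there is no stated figure to reproduce here and every input except the group size is an assumption.

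- n = 100 analysed per arm (Protocol, 2. Sample Size); two-sided 5% test (assumed); no true intervention effect
- control success p0 = 0.20; SD of a child's four-month mean monthly gain = 120 g; UC difference d = 30 g/month in favour of the intervention UCs (all assumed)

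Normal model: p0 = P(Z > z0), so z0 = 0.842. With the shift, p1 = P(Z > z0 − d/SD) = P(Z > 0.842 − 0.250) = P(Z > 0.592) = 0.277. The area difference alone moves the success proportion by 7.7 percentage points.

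Rejection probability of the two-proportion test:

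- mean proportion = (0.200 + 0.277)/2 = 0.2385
- SE under equality = √(2 × 0.2385 × 0.7615/100) = 0.0603
- SE under the shift = √(0.200 × 0.800/100 + 0.277 × 0.723/100) = 0.0600
- P(Z > (1.96 × 0.0603 − 0.0771)/0.0600) = P(Z > 0.684) ≈ 0.247

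About 25% of trials would reject with no intervention effect, against a nominal 5%.

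**Step 4. Sensitivity to the assumptions.** Same model, p0 from 10% to 30%, SD from 100 to 150 g:

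| Assumed UC difference | Rejection with no true effect |
|---|---|
| 5–10 g/month | 5.2% to 8.4% |
| 20–50 g/month | 8.8% to 79% |

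The answer runs from negligible to dominant according to a UC difference that the protocol does not give. The calculation shows what an area difference would do; it is no evidence that one exists. With the mid-case inputs and 200 per arm, rejection rises to about 44%, so a larger sample does not help.

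**The case against.** The strongest reply is that the protocol is open about its design. Nothing in it calls the study randomised, it says outright that the areas were chosen purposively, and the Consent Process section describes a study to test feasibility. Community sensitization is delivered to whole intervention clusters, so keeping the arms in separate areas is understandable. Non-randomised area comparisons are a recognised design. All of this stands as a defence of the design. It does not cover the conclusion: the Study Overview sets a primary between-arm hypothesis, the Sample Size section attaches 80% power to it, and the Evaluation section speaks of effectiveness without qualification.

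It can also be said that covariates and sensitivity analyses belong in a statistical analysis plan, which is not shown. That is fair for the detail. The choice of areas is fixed in the protocol, however, and no later plan can separate UC from arm.

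Four stronger readings are tempting, and the document does not support them.

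- *A reader might infer that the result will be biased towards the intervention.* Direction is unknown: higher need could slow growth or leave more room to gain.
- *A reader might infer that the intervention UCs are needier than the control UCs.* Need is given as a reason for choosing the former; no comparison with the latter is made.
- *A reader might infer that only the intervention arm had earlier exposure.* The control UCs' formative-phase status is not stated. Moreover, the protocol's summary of the intervention gives this aim for the earlier work: "to learn what is already possible within the community of Rahim Yar Khan and to amplify these strategies to the wider community". The amplifying is reserved for the later phase, so the formative work was not described as teaching mothers.
- *A reader might infer that the six UCs must be re-allocated by lot.* That is a debatable redesign. The areas were chosen partly for existing engagement, so it is not free. With C(6,3) = 20 allocations the smallest two-sided permutation p-value is 2/20 = 0.10.

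**Conclusion.** The point holds as one of identification and interpretation. The intervention UCs were selected on features that may bear on the outcome, the control UCs have no stated basis or formative-phase status, and no UC holds both arms. An intervention effect therefore cannot be told apart from UC differences or, if the control UCs were not equally engaged, from earlier contact with the study. This follows from the text and needs no numerical assumption.

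The size is unknown. The 25% figure rests on assumed 20% control success, SD 120 g and a 30 g/month UC difference; with differences of 5–10 g/month the excess over 5% is small. It should be quoted only as an illustration.

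The matter should be corrected before the trial reports, because it governs what the primary comparison can claim.

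**What to change.** 1. In the Study Overview (primary hypothesis and Objective 4(b)) and the Evaluation section, describe the between-arm analysis as a non-randomised area comparison, and limit the conclusion to an association that may be confounded by area.
2. Make the primary between-arm contrast one adjusted for baseline weight, age, sex, wealth class and food-security category, using data collected at screening or baseline. State that this reduces confounding but cannot remove it at UC level, and that wealth class is itself community-defined.
3. Record the formative-phase status of every UC and village in both arms, and state how the control UCs were chosen.
4. Report baseline characteristics by UC as well as by arm.
5. Repeat the primary contrast by previous engagement, or without previously engaged villages, as a sensitivity analysis.

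The cost is protocol wording, one exposure field per village and modest extra analysis. The downside is a more modest claim. The sensitivity analysis may also lose much of its sample: engagement was a reason for choosing the intervention UCs, and the protocol does not say how many villages were engaged. Random re-allocation of the six UCs is not required.
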